domains by using latent profile analysis. Profile 5 (black line, **Figure 1**) was the most atypical, and it was characterized by exaggerated scores for arousal, excitability, hypertonicity, quality of movement, and stress abstinence, relative to four other distinct profiles. Researchers have associated Profile 5 with early childhood outcomes, including more externalizing behavior problems, internalizing behavior problems, and total behavior problems at age three, as well as lower IQ scores after adjustment for gestational age and socioeconomic status (27). In this protocol, “atypical neurobehavioral profile” refers to Profile 5 in **Figure 1**.

There is a lack of consensus on the effects of prenatal opioid exposure on neurodevelopmental outcomes in early childhood. A recent comprehensive review indicated that there are discrepant findings with respect to the presence or absence of altered neurodevelopment with in-utero exposure (28). This reflects that many studies are small and cannot adjust for potential confounding variables. Potential confounding variables (e.g., prenatal exposures to other substances, nutrition, socio-economic status, medical complications, poor prenatal care) may all impact early childhood development. Few studies have examined neurodevelopment among infants who develop NOWS, and even less among infants who are pharmacologically treated for NOWS. A retrospective chart review of infants born in 2011-2015 and treated for NOWS with morphine, methadone or buprenorphine had lower Bayley Scales of Infant Development III at 23 months compared with normative data for the Bayley Scales (29). Contemporary data on early childhood neurodevelopment of infants with NOWS in the presence or absence of pharmacologic treatment remains a major research gap.

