5.1.3. Other Collected Data

Initial descriptive analyses will include weaning intervention group characteristics. We will collect data to characterize the following.

- Stratification data
- Hospital variables: participation in ESC
- Maternal variables (e.g., socioeconomic status, obstetric complications, opioid medication, medication assisted treatment program, non-opioid drugs, cigarettes, alcohol, selective serotonin reuptake inhibitors, and psychiatric diagnoses)
- Infant demographics at birth (e.g., gestational age, birth weight, sex, multiples, growth parameters, out-born, and location of care)
- Characteristics of NOWS treatment (e.g., stabilization dose, age at stabilization, use of adjunctive drugs to the primary NOWS drug treatment)
- Infant characteristics at the start of the intervention (e.g., weight, postnatal age) and when medically ready for discharge per the hospital standard.

We will include the stratification variable (hospital) in regression modeling as a random effect, and we will include stabilization dose and maternal treatment as covariates. With respect to maternal treatment, it will be a categorical variable with four categories:

- 1) Methadone use
- 2) Buprenorphine \pm naloxone
- 3) Prescribed opioids other than methadone and buprenorphine \pm naloxone
- 4) Non-prescribed opioids

There will be some mixing among these four groups; therefore, we will use the following rules to classify infants:

- If methadone is used with other opioids, classify as methadone.
- If buprenorphine is used with other opioids, classify as buprenorphine \pm naloxone.
- If methadone is used with buprenorphine, classify based on which drug has been in use for a longer time interval.

Depending on the descriptive comparisons across weaning intervention groups, we may add other variables to the regression models such as medication assisted treatment programs. If the difference of a variable across the weaning intervention is statistically significant at a two-sided alpha of 0.05, then we may include the variable as a covariate in the regression models. Beyond the significant difference, we will consider other factors, such as the type of analysis, correlation with other variables in the model, and trial subcommittee discussion about the nature of the potential covariate.

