We will provide the mean and SD of infants' weights (z-scores) separately for each treatment group. We will use a mixed linear model to evaluate the effect of treatment arm on weight (z-scores). The model will examine how the treatment means differ (i.e., main treatment effect), how treatment means change over time (i.e., main time effect), and how differences between treatment means change over time (i.e., treatment-by-time effect). We will carry out assessment across 3 time points: birth, hospital discharge, and 24 months of age. The mixed model longitudinal analytical approach allows us to analyze correlated data obtained repeatedly from the same participant and account for the ICC among participants nested within with same clinical site. To account for potential imbalance in key demographic and site-level characteristics, unadjusted and adjusted GLMMs will be fit to the data. Initially, the unadjusted mixed model will include the fixed categorical effects of intervention, time, and intervention-by-time interaction and the random-site effect. We will calculate the point estimates and their respective CIs for the changes in infants' weights for each intervention group and for the difference in the estimated change between intervention groups. Additionally, the team will present the p-value of the difference in point estimates between intervention groups.

We will examine the impact of the treatment arm on length, HC, and infant weight for length (z-scores) using the same analytical methods described for weight (z-scores) above. Additionally, we will provide the mean and SD of infant BMI-z at 24-months for each treatment group. The team will use a GLMM with an identity link to compare average BMI-z between the groups, and the team will report point estimates for the group mean difference along with a 95% CI.

To compare Bayley-IV scores between intervention arms, we will perform a linear mixed-effects model with a fixed effect for the intervention group and a random effect for study site. We will report point estimates for the group mean difference along with a 95% CI, and the team will repeat this analytical approach for each of the Bayley-IV domains.

Descriptive statistics (means, medians, SD, percentiles) for continuous secondary outcomes and frequency based statistics (N and percentages) for binary secondary outcomes will be generated and summarized in a tabular form by treatment group.

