A difference of 2.0 days in the length of treatment represents the minimum clinically important treatment effect for clinical care. If we can demonstrate a 2.0-day difference, there will likely be a reduction in hospital resources (bed, nursing, pharmacy, and physician) and cost. In addition, this effect size should facilitate a faster transition out of the hospital and keep the maternal-infant dyad together in a better environment than a hospital. The proposed intervention difference is similar to a recent trial comparing morphine to methadone (18). Group sample sizes of 251 infants per treatment arm (total enrollment, 502 infants) will achieve 90% power to reject the null hypothesis of equal means when the population difference is 2.0 days with a standard deviation of 6.9 days and with a significance level of 0.05 using a two-sided two sample t-test. If the standard deviation is as high as 8.0 days, a similar sample size will achieve 80% power to reject the null hypothesis using a two-sample t-test and a two-sided significance level of 0.05.

With respect to analysis of the Bayley IV at 24 month follow-up, if the FU is at least 60%, then with a two-sided alpha of 0.05 we will be able to detect a difference in any composite score of 5.7 or greater with at least 80% power and will be able to detect a difference in any scaled score of 1.06 with at least 80% power.

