6.4.3 Covariates

All secondary regression models will include the stratification variable (site) as a random effect and will be adjusted for:

- Breastfeeding status
- Stabilization dose, continuous
- Maternal treatment which will be categorized as follow:
 - Methadone use
 - o Buprenorphine ± naloxone
 - Prescribed opioids other than methadone and buprenorphine ± naloxone
 - o None/Unknown

In case of mixing among the 4 groups the following rules will be followed:

- o If methadone is used with other opioid, classify as methadone
- If buprenorphine is used with other opioid, classify as Buprenorphine ± naloxone
- o If methadone is used with buprenorphine, classify based on which drug has been used most proximal to delivery.

Additionally, if the sample size allows, secondary analyses can be adjusted for critical covariates that are substantially imbalanced at baseline (both clinically and statistically significantly different)

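### Naming socioeconomic status and gestational age in advance in the 24-month Bayley and BITSEA models would bring a modest gain in precision

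*Protocol*

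**What the plan says.** Protocol 3.3.2, discussing why studies of prenatal opioid exposure disagree, states: "Potential confounding variables (e.g., prenatal exposures to other substances, nutrition, socio-economic status, medical complications, poor prenatal care) may all impact early childhood development". Socioeconomic status is in that list and gestational age is not. Gestational age appears in the same section only as an adjustment variable, beside socioeconomic status, in a cited analysis of neurobehavioural profile and IQ.

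Both variables are collected. Protocol 5.1.3 lists "Maternal variables (e.g., socioeconomic status, obstetric complications, opioid medication, medication assisted treatment program, non-opioid drugs, cigarettes, alcohol" and, under infant demographics at birth, gestational age.

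The models are as follows.

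- Bayley, protocol 5.1.5: "we will perform a linear mixed-effects model with a fixed effect for the intervention group and a random effect for study site". No other covariate is given.
- BITSEA, protocol 5.1.5: arm, the stratifying variable, maternal treatment and stabilization dose.
- SAP 6.4.3, for every secondary outcome: "All secondary regression models will include the stratification variable (site) as a random effect and will be adjusted for" breastfeeding status, stabilization dose and maternal treatment. SAP 4.1 assigns H12d a linear mixed model by name. It does not list H13, whose covariates follow from the general rule in 6.4.1 and 6.4.3.

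Further covariates may be added under SAP 6.4.3 if the sample size allows and if they differ at baseline both clinically and statistically. Protocol 5.1.3 has a similar rule based on a significance test.

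SAP 6.6.2 covers missing follow-up data. It plans a logistic model of missingness on participant characteristics, exploration of multiple imputation above a threshold such as 5% missing, selection models, and sensitivity analyses. It does not name the variables in these models.

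**The concern.** The usual reason to adjust a randomised comparison is to remove outcome variance explained by baseline variables known to predict the outcome. Here one covariate set serves all secondary outcomes, and it describes opioid exposure, dose and feeding. For development at 24 months the protocol itself points to socioeconomic status, and that variable is on file, yet the plan does not commit to using it.

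The only way in is a test of baseline imbalance. A variable can be well balanced and strongly prognostic, and this rule would leave it out although adjusting for it would narrow the interval. The rule is also applied after the baseline data have been seen.

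The width of the interval for the arm difference in Bayley and BITSEA scores is what is at stake. Follow-up may be as low as 60% and the target sample has been reduced, so these intervals will be wide in any case. A second, conditional matter is loss to follow-up: if it depends on family circumstances, it matters whether those circumstances are in the missing-data models.

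**Working it through.** **Inputs from the documents.** Protocol 5.2.3: "if the FU is at least 60%, then with a two-sided alpha of 0.05" the trial can detect "a difference in any composite score of 5.7 or greater with at least 80% power", within a plan for 502 infants. SAP 3.4: target lowered to 302. No Bayley SD and no R² for any covariate is given.

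**Assumed.** Composite SD 15 and scaled-score SD 3. The share of variance explained by the two variables beyond the existing covariates (incremental R²) is taken as 5%, 10% or 20%. SD 15 is read as the SD left after the existing covariates. If they explain something, every figure below shrinks in proportion.

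**The plan's own figure.** Detectable difference = (1.960 + 0.842) × SD × √(4/N), with N = 0.60 × 502 = 301.

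- Without an SD, 5.7 cannot be reproduced. It would imply SD = 5.7 / (2.802 × √(4/301)) = 17.6. The scaled-score figure of 1.06 would imply SD 3.28.
- At SD 15 and 3 the detectable differences are 4.84 and 0.97. Power is 0.91 at 5.7 and 0.87 at 1.06, so the claim of at least 80% is met at 502 infants.

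**At the target of 302.** N = 0.60 × 302 = 181. The detectable difference is 2.802 × 15 × √(4/181) = 6.25, or 6.28 with the t distribution. Power at 5.7 is 0.72.

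**Adding covariates.** Multiply the detectable difference by √(1 − R²). The equivalent gain in children is 1/(1 − R²) − 1.

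| Incremental R² | Factor | Detectable difference (from 6.28) | Power at 5.7 | Equivalent extra children |
|---|---|---|---|---|
| 0 | 1 | 6.28 | 0.72 | – |
| 5% | 0.975 | 6.12 | 0.74 | 5% |
| 10% | 0.949 | 5.96 | 0.76 | 11% |
| 20% | 0.894 | 5.62 | 0.81 | 25% |

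At the implied SD of 17.6 the starting value is 7.35, falling to 7.16, 6.97 and 6.57. For the BITSEA the documents give neither an SD nor a target difference, so only the proportional factors carry over.

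**For scale.** Going from 502 to 302 raises the detectable difference by √(301/181) = 1.29, or 29%. The largest gain in the table is 10.6%.

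**Loss to follow-up.** A simulation used 4,000 replicates, 502 randomised, about 60% followed, SD 15, no true effect, and socioeconomic status explaining 5% to 20% of variance.

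- Follow-up related to socioeconomic status equally in both arms: bias about zero (at most 0.05 points, which is simulation error).
- Log-odds slopes of 0.8 in one arm and 0.2 in the other: unadjusted bias of 0.7 to 1.4 points in size.
- Slopes of 1 and 0: 1.1 to 2.3 points.
- Adjusting for socioeconomic status: within 0.04 points in every case.

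A hand example gives a similar size. Suppose half the families have low socioeconomic status, with an 8-point gap. Follow-up is 50% (low) and 70% (high) in one arm, and 60% for both in the other. The low share among those followed is 0.25/0.60 = 41.7% against 50%, so the shift is 0.083 × 8 = 0.67 points. The standard error at N = 181 is 15 × √(4/181) = 2.23, so this is 0.3 standard errors.

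**The case against.** Several points count against making much of this, and most of them stand.

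- **A reader might infer that the treatment comparison is confounded.** It is not. The list in protocol 3.3.2 explains disagreement among observational studies. Randomisation stratified by hospital removes confounding whether or not these variables are in the model.
- **A reader might infer that loss related to these variables goes uncorrected.** SAP 6.6.2 does not support that. It plans missingness modelling, imputation and sensitivity analyses, and 40% missing would far exceed its example threshold of 5%. The remaining gap is that predictors are not named and imputation of outcomes is only to be explored.
- **A reader might infer that the protocol calls both variables drivers of development.** It says only that the listed factors may affect it, and gestational age is not listed. Its range is also narrow: entry is at 36 weeks or more, and the chart review in Appendix 1 has an SD of 1.3 weeks. Its gain may be small.
- **Dropout bias needs a particular pattern.** The dependence on socioeconomic status must differ by arm. Parents, clinicians, research staff and the Bayley examiner are blinded, which makes this less plausible.
- **The existing covariates may already carry part of the information.** Hence only incremental R² counts, and the documents give none.
- **These are exploratory outcomes.** SAP 6.4.4 treats everything but the primary analysis that way. SAP 6.4.2 also foresees cutting covariates if models fail to converge.

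The conditional route to adjustment is real but does not answer the precision point, because it selects on imbalance and not on prognosis.

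**Conclusion.** The 24-month models do not pre-specify two collected baseline variables, one of which the protocol says may affect early development. Some precision is therefore forgone. On assumed incremental R² of 5% to 20%, the detectable Bayley difference falls from about 6.3 to between 6.1 and 5.6 points, a gain of 2.5% to 10.6%. Socioeconomic status has the stronger case.

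These figures rest on 302 infants, 60% follow-up and SD 15. The SAP reports that the trial was to be terminated after December 31, 2023 and does not give final enrolment. A smaller sample would widen every interval, but the proportional gain would stay the same.

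This is an optional precision improvement to secondary, exploratory outcomes. It is not an error in the plan, and the omission alone introduces no bias.

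**What to change.** Before the second-phase analysis, which SAP 3.7 expects to begin in July 2026:

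1. In SAP 6.4.3, for H13 (Bayley cognitive, language and motor) and H12d (BITSEA), name as fixed covariates, whatever the baseline balance, the maternal socioeconomic variable already collected and gestational age (continuous). State which data field is meant, since the documents say only socioeconomic status.
2. In SAP 6.6.2, include both in the missingness model and in any imputation model for these outcomes.
3. Keep the protocol's arm-plus-site model as the unadjusted result.

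The cost is a few degrees of freedom and some missing socioeconomic values to impute. No new data are needed. The amendment should be dated before the follow-up data are analysed.

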3.3.3. Preliminary Data

Pilot Clinical Data. The ISPCTN and the NRN have undertaken a retrospective chart review to inform the design of clinical trials for infants with NOWS (Advancing clinical trials in neonatal opioid withdrawal syndrome [ACT NOWS] current experience: Infant exposure and treatment). Investigators reviewed medical records for infants ≥ 36 weeks gestational age and born between July 1, 2016 through June 30,

2017, and mothers medical records, when available, when there was opioid use, determined by maternal history, maternal/infant toxicology screen, or NOWS scoring. Data were collected from 1808 infants at 23 of 28 ISPCTN sites and two of five NRN sites. The ACT NOW Current Experience infant characteristics and demographics are presented in **Appendix 1** and infant pharmacological treatment are presented in **Appendix 2**.

The salient findings from the preliminary data of the ACT NOW Current Experience retrospective chart review were:

- 1) Of infants evaluated for NOWS, medical professionals treated 38.6% with pharmacologic therapy.
- 2) Of infants treated with pharmacological therapy, the primary medications to control NOWS signs were morphine (86.1%) and methadone (12.9%).

Site Practice for Weaning Strategies of Pharmacological Treatment for NOWS: Multiple clinical guidelines from IDEa States Pediatric Clinical Trials Network and the Neonatal Research Network were reviewed to understand the extent of variation in weaning strategies for morphine and methadone. Among centers that use morphine, weaning strategies included reduction by a fixed dose (n=2), 10% of the stabilization dose (n=6), or 10-20% of the stabilization dose (n=3). Among centers that use methadone, weaning strategies included reduction by a fixed dose with changes in frequency of dosing (n=2), reductions by 10% of that stabilization dose (n=1), and reductions by greater than 10% of the stabilization dose (n=3). This review supports a wide range of clinical practices for pharmacologic treatment of NOWS.

Site Practice after Cessation of Pharmacological Treatment for NOWS. Seventeen ISPCTN and NRN sites submitted guidelines and protocols they use to treat infants with NOWS (morphine use: 12 sites, methadone use: 5 sites). In eight of the 17 guidelines, there were specific directives that clinical teams should monitor NOWS infants receiving pharmacological therapy in the hospital for at least 48 hours after treatment cessation. In the other nine guidelines, there were no comments on the duration of observation after pharmacological treatment cessation.

NOWS Infants Cost of Care. Data was obtained from one ISPCTN site to provide an estimate of the costs of care for NOWS infants. The cost was \$869 per day per infant, which represents the average daily cost among 86 infants born between October 2017 and September 2018. Infants had an average length of hospital stay of 19.4 days, and medical professionals cared for these infants in a family care center that was part of a newborn nursery. The family care center promotes non-pharmacological therapy for newborns exposed to opioids and provides the opportunity for mothers to room in and breast-feed, if there are no contraindications. Costs at hospitals that care for opioid-exposed infants in the NICU may be substantially higher.

3.3.4. Rationale and Summary

Medical professionals pharmacologically treat NOWS infants when non-pharmacological therapy is inadequate to control NOWS signs. The survey data indicate that medical professionals pharmacologically treat a substantial proportion of NOWS infants. There are heterogeneous practices in all aspects of pharmacological treatment (treatment thresholds, initiation, medication type, initial dose, second-line and third-line medications, weaning algorithm, and home therapy). One trial cannot address all the knowledge gaps, and there is limited evidence to guide current clinical management. Clinical trials for this group of patients are challenging for multiple reasons. First, multiple prior randomized trials

closed before meeting the projected sample size due to an inability to enroll subjects (15, 17, and 18). Second, hospitals and medical professionals vary in their NOWS treatment practices. Third, although a larger number of hospitals use morphine to treat NOWS, recent clinical trial data suggests that medical professionals may shift to using methadone as the primary opioid for NOWS treatment (18).

Given the uncertainty of the specific opioid medical professionals will use to treat NOWS in the future, the ideal clinical trial would inform clinical practice for the use of either morphine or methadone. To that end, the proposed study is a pragmatic trial to determine whether a rapid-weaning intervention reduces the number of days of opioid treatment, compared to a slow-weaning intervention, and we powered the proposed study to detect a two-day difference in the length of treatment. Hospitals will be able to use either morphine or methadone with the knowledge that we may find a positive treatment effect for both, one, or neither drugs. We are planning secondary analyses to separately examine the results for each opioid.

The rapidity at which a clinical team can perform weaning with infant tolerance without recurrence of NOWS signs is unknown. In a randomized trial of morphine versus methadone in which clinical teams weaned the drug by 10% of the stabilization dose (18), 48% of morphine-treated and 38% of methadone-treated infants needed dose escalation. With progressive increases in the percent reduction of drug dose, there will, presumably, be an increase in frequency of recurrence of NOWS signs that will mitigate the benefits of more rapid weaning. A 15% reduction of drug dose is large enough to yield important decreases in the length of treatment, which may enable earlier transition out of the hospital and decreasing healthcare costs.

Shortening the weaning phase of NOWS treatment has the potential to impact healthcare costs and minimize the separation of the mother-infant dyad. Opioid use disorder is estimated to occur in 6.5/1000 hospitalizations for infant delivery (30). This allows an estimate of cost savings for infant's ≥ 36 weeks gestations:

- Births per year in the US: $\approx 4,000,000$ births
- Percent births ≥ 36 weeks: $\approx 90\% \times 4$ million $\rightarrow 3,600,000$
- Opioid exposed: 6.5/1,000 deliveries
- Total opioid exposed: $6.5 \times 3600 \rightarrow 23,400$
- Opioid exposed receiving pharmacological treatment: $38.6\% \times 23,400 \rightarrow 9032$
- Cost of care/day: $\$869 \times 9032 \rightarrow \$7,848,808$

A treatment reduction of 2.0 days would reduce healthcare costs by more than \$15.7 million per year across the United States. Potential cost savings would be even greater for hospitals that care for infants with NOWS in facilities with higher levels of care (e.g., NICU, special care nurseries).

If successful, this clinical trial would achieve the overarching goals of research initiatives for NOWS (8). Specifically, it would limit ongoing opioid exposure for infants, minimize separation of the mother-infant dyad, and reduce healthcare expenditures.

SECTION 4. METHODS

